6.2.6. Exploratory Efficacy Endpoints

A complete list of exploratory endpoints will be provided in the reporting and analysis plan (RAP).

6.3. Safety

The timing for all safety assessments is outlined in the Time and Events Schedule [Table 5](#).

Maternal:

- Incidence of reported AEs and SAEs
- Significant changes in vital signs and clinical laboratory tests
- Incidence of treatment-limiting toxicities including both clinical and laboratory etiology causing subject to discontinue study treatment

- Maternal AEs of special interest
 - Maternal death
 - Chorioamnionitis and its complications
 - Clinical chorioamnionitis, PPROM, endomyometritis, wound infection, pelvic abscess, bacteremia, septic shock, disseminated intravascular coagulation, and adult RDS
 - Placental abruption
 - Postpartum hemorrhage - postpartum hemorrhage and/or retained placenta (as assessed by AEs, time to expulsion of the placenta, assessment of uterotonic agents used, and change in hemoglobin from baseline value to 24 to 48 hours post-delivery adjusting for mode of delivery)
 - Pulmonary edema
- Incidence of women scoring 12 or higher on the EPDS

Fetal:

- Incidence of reported AEs, including SAEs
- Fetal acidosis
- Fetal AEs of special interest
 - Intrauterine fetal demise
 - Category II or III fetal heart rate tracing (defined according to ACOG Practice Bulletin 106 [[ACOG](#), 2009])
 - Fetal inflammatory response syndrome characterized by cord blood interleukin-6 >11 pg/mL, funisitis, or chorionic vasculitis

Neonatal:

Note: Information collected from the time of birth through 28 days post EDD.

- Neonatal Apgar scores (at 1 and 5 minutes after birth), growth parameters (weight, length, and head circumference) at birth and at discharge, and documentation of any complications
- Incidence of reported AEs and SAEs
- Neonatal AEs of special interest are of interest because of their relationship to maternal chorioamnionitis and will include the following:
 - Neonatal death
 - Asphyxia
 - Infections (early onset neonatal sepsis, septic shock, pneumonia, meningitis)
 - RDS
 - Hypotension

- IVH/periventricular leukomalacia with cysts or porencephaly
- Bronchopulmonary dysplasia
- Neonatal acidosis
- Hyperbilirubinemia
- Necrotizing enterocolitis (any modified Bell's staging criteria)
- Hypoxic ischemic encephalopathy

Maternal and neonatal disease-related events (DREs) to be reported are described in Section 6.3.7.

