3.1.4. Delivery Phase

Operational procedures will be instituted to optimize data collection and reporting consistency in those situations where the subject's delivery is performed by her referring primary care obstetrician. These procedures include identification at conclusion of Inpatient Randomized Treatment Phase of the intended delivery caregiver, ensuring the delivery caregiver or neonatal intensive care unit (NICU) staff understand the information needed for the study, those events that require rapid communication to clinical investigators, and a process that ensures clinical investigators can contact the appropriate personnel in case of follow-up questions.

For subjects who deliver at the investigative center, a placental tissue sample will be obtained at the time of delivery for central histopathologic examination and a cord blood sample will be collected for potential genetic research and biomarker assays. If delivery occurs within 12 hours of IP completion or discontinuation, the cord blood sample will also be used for the PK assessment (see SPM for information about how these samples will be collected), and, if required, a corresponding maternal blood sample will be collected for PK analysis (see Section 6.5.1). In addition, a breast milk/colostrum sample will be collected for PK analysis in women who deliver at the investigative center and produce breast milk within 12 hours after IP completion or discontinuation (see Section 6.5.3).

The following information regarding the delivery and hospitalization for mother and newborn will be obtained through a review of the hospital records:

- Date and time of delivery
- Mode of delivery
- Indication for delivery
- Concomitant medications
- Maternal AEs and serious AEs (SAEs) (including AEs of special interest; Section 6.3.2.3)
- Maternal health care resource use

The newborn medical records will also be reviewed in order to record the following:

- Variables relevant to the composite
- Apgar scores at 1 and 5 minutes
- Length, weight, and head circumference
- Blood gases (when available)

- Hospital length of stay
- Neonatal health care resource use
- Neonatal AEs and SAEs; in particular, the review will focus on any complications requiring intensive or specialized care and information specific to complications of prematurity will be collected (see Section [6.3.2](#) and Section [6.3.7.2](#)).

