25. A breast milk/colostrum sample is only to be collected in women who deliver and produce breast milk within 12 hours after completion or discontinuation of the IP.
26. A placental tissue sample will be collected at delivery in subjects who deliver at an investigative center.
27. A maternal blood sample for genetic research will only be collected from subjects who provide separate informed consent (see [Appendix 1](#)).
28. A cord blood sample will be collected in subjects who deliver at an investigative center, if additional consent is provided.
29. Testing for fetal fibronectin will be performed only at those institutions collecting the information as routine practice. Fetal fibronectin will not be used to determine study eligibility.
30. Cervical length measured by transvaginal ultrasound will be captured only at those institutions collecting the information as routine practice. Cervical length will not be used to determine study eligibility.

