6.8. Biomarkers

A biomarker is a molecule associated specifically with a disease or condition such that it allows for the diagnosis, risk identification, or optimization of treatment. A maternal blood sample for biomarker research will be collected at Screening and a cord blood sample for biomarker research will be collected during the Delivery Phase. The samples will be stored and may be analyzed for future exploratory research.

The blood samples collected for biomarker analyses are summarized further in [Appendix 5](#).

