8.3.5.2. Safety Analyses

No formal hypothesis statistical test will be performed for the safety data. All safety analyses will be done using the safety population, unless otherwise specified. The objective of the safety analysis is to describe the maternal, fetal, and neonatal safety profile during/after IV retosiban treatment as compared with atosiban treatment. As such, maternal, fetal, and neonatal safety data will be summarized by treatment group.

All summary statistics of continuous variables will include: n, mean, median, standard deviation, minimum, and maximum. For binary outcomes, all summary tables will include the number and percentage of subjects with the response/event. All summary tables will include N for each group (i.e., the total number of subjects randomly assigned to each group within the appropriate population).

To further describe the maternal, fetal, and neonatal safety profile of retosiban, the following subgroups may be explored:

- GA of pregnancy at randomization
- Established progesterone use
- GA at delivery
- Maternal age
- Region/site

For each subgroup, maternal, fetal, and neonate safety data will be summarized by treatment and subgroup, as described above.

8.3.5.2.1. *Extent of Exposure (Maternal)*

The total volume administered during the infusion and the total volume administered overall will be summarized. If applicable, the number of infusion interruptions and the time taken for each infusion will be summarized. The frequency and percentage of women who discontinued study treatment and reason for discontinuation and who increased study treatment from 6 to 12 mg will be summarized.

8.3.5.2.2. *Adverse Events*

Adverse events will be coded using the MedDRA dictionary and grouped by body system. Adverse events will be summarized by treatment group. Within each group, AEs will be summarized by frequency and proportion of total subjects, by event type, and by category of body system. Separate summaries will be given for all AEs, drug-related AEs, SAEs, and AEs leading to discontinuation. Where appropriate, each phase of the study (pretreatment, treatment, and follow-up) will be tabulated separately.

The proportion of subjects reporting at least 1 AE, 1 IP-related AE, 1 SAE, and 1 AE leading to discontinuation will also be calculated for each group.

Adverse events of special interest (see Section 6.3.2.3) and DREs (see Section 6.3.7) will be similarly summarized.

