8.4. Biomarker Analyses

FFN results and cervical length will be presented in the baseline characteristics table. Also, the results will be listed. If applicable, inflammatory biomarker such as IL-6 will be summarized and listed.

Whenever applicable, the details of these additional analyses to explore the correlation of biomarker and the study effect will be described in a separate document.

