3.403	Maternal Safety		Summary of Observed Value and Change from Baseline in Clinical Chemistry by Visit		

CONFIDENTIAL

GSK200721

Safety Tables					
No.	Population	IDSL / TST ID / Example Shell	Title	Programming Notes	Deliverable [Priority]
Vital Signs					
3.421	Maternal Safety		Summary of Observed Value and Change from Baseline in Maternal Vital Signs by Visit		
3.424	Maternal Safety		Summary of Fetal Heart Rate Category		
Neonatal Hospital Admission					
3.463	Neonatal Safety		Summary of Neonatal Hospital Unit Utilization At Birth		
3.464	Neonatal Safety		Analysis of Length of Neonatal NICU Stays At Birth		
Maternal Placental Data					
3.501	Maternal Safety		Summary of Placental Findings		

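### Fetal inflammatory response syndrome needs a cord or placental specimen taken at the study center, but it is reported over all treated women, so unsampled women count as event-free

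*Protocol*

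**What the plan says.** **Definition.** Protocol Section 6.3 and SAP Section 8.2.3.6 define fetal inflammatory response syndrome (FIRS) in the same way: "Fetal inflammatory response syndrome characterized by cord blood interleukin-6 >11 pg/mL, funisitis, or chorionic vasculitis". The first criterion needs cord blood; the other two need histology of the cord or placenta.

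**Who is sampled.** Protocol Table 5, footnote 26: "A placental tissue sample will be collected at delivery in subjects who deliver at an investigative center". Footnote 28: "A cord blood sample will be collected in subjects who deliver at an investigative center, if additional consent is provided". Sections 3.1, 3.1.4 and 6.5.2 and Appendix 5 repeat the limit to investigative-center deliveries. Off-site birth is foreseen: Section 3.1.4 sets up procedures for cases where "delivery is performed by her referring primary care obstetrician".

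**Whether interleukin-6 (IL-6) is assayed.** Protocol Section 6.8: "The samples will be stored and may be analyzed for future exploratory research". SAP Section 8.4: "If applicable, inflammatory biomarker such as IL-6 will be summarized and listed". SAP Appendix 11, which says that only the displays it lists will be produced, names none for IL-6.

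**How the event is reported.** Protocol Section 8.3.5.2: "AEs will be summarized by frequency and proportion of total subjects", with N the whole group within the population. SAP Section 8.2.3.6 treats events of special interest in the same manner as all adverse events, that is, as number and percentage of subjects. Table 3.171 uses the Maternal Safety Population, and Table 3.172 splits it by gestational age group.

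**Placental findings.** Table 3.501, "Summary of Placental Findings", carries the Maternal Safety label but states no percentage denominator. SAP Section 8.2.8 plans these findings by gestational age at randomization and by time from start of treatment to delivery.

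**The concern.** Nothing in the plan separates a woman who was examined and found negative from one whose cord and placenta were never examined. Both enter the denominator of Table 3.171, and neither enters the numerator. The reported percentage is therefore the true risk multiplied by the share of women sampled.

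That share need not be equal between arms. A birth during the inpatient treatment phase should ordinarily be on site, whereas a woman discharged undelivered may give birth elsewhere. A drug that prolongs pregnancy could thus reduce the share sampled in its own arm.

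The event bears on a risk that the protocol names. Table 1 (Section 1.3.1) lists harm from prolonging pregnancy in the presence of subclinical intrauterine infection, notes that such infection may be asymptomatic, and includes placental sampling among the mitigations. SAP Section 9 drops the covariate analysis of subclinical infection, which leaves more weight on FIRS and the placental table.

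**Working it through.** The documents give no FIRS rate, on-site delivery rate or evaluable number, so there is no figure of the plan's own to reproduce. A simple ascertainment model shows the size.

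**Inputs**
- Share of atosiban women delivering within 3 weeks, p_A = 0.55 (Protocol Section 8.2.1, a design assumption).
- The same share for retosiban, p_R = 0.30 to 0.45 (assumed here).
- Probability of on-site, sampled delivery: e = 0.70 to 1.00 if within 3 weeks, l = 0.30 to 0.90 if later (assumed here).
- No FIRS is recorded for an unsampled woman.

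**Formula.** Share sampled S = p × e + (1 − p) × l. If true risk is equal in the arms and unrelated to timing, the apparent relative risk (RR) over all women is S_R / S_A.

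| p_R | e | l | S_A | S_R | Apparent RR |
|---|---|---|---|---|---|
| 0.45 | 1.00 | 0.90 | 0.955 | 0.945 | 0.99 |
| 0.40 | 0.95 | 0.50 | 0.7475 | 0.680 | 0.91 |
| 0.30 | 0.95 | 0.30 | 0.6575 | 0.495 | 0.75 |
| 0.40 | 0.80 | 0.80 | 0.800 | 0.800 | 1.00 |
| 0.45 | 0.70 | 0.90 | 0.790 | 0.810 | 1.03 |
| 0.30 | 0.70 | 0.90 | 0.790 | 0.840 | 1.06 |

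The second row in full: 0.55 × 0.95 + 0.45 × 0.50 = 0.7475; 0.40 × 0.95 + 0.60 × 0.50 = 0.680; 0.680 / 0.7475 = 0.91. If p_R also equals 0.55, the RR is 1.00 whatever e and l are.

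**Understatement within each arm.** In the second row the reported incidence is too low by 1 − 0.7475 = 25% for atosiban and 1 − 0.680 = 32% for retosiban.

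**Masking of a true excess.** A true RR of 1.50 would show as 1.50 × 0.680 / 0.7475 = 1.365 in the second row and 1.50 × 0.495 / 0.6575 = 1.129 in the third.

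**Does an evaluable-only denominator cure it?** If risk is unrelated to timing, yes: the RR returns to 1.00 in every row. If risk depends on timing, no. Assume 25% for early and 8% for late births, with p_R = 0.40, e = 0.95 and l = 0.50:
- True: (0.40 × 0.25 + 0.60 × 0.08) / (0.55 × 0.25 + 0.45 × 0.08) = 0.148 / 0.1735 = 0.85.
- All women: (0.40 × 0.95 × 0.25 + 0.60 × 0.50 × 0.08) / (0.55 × 0.95 × 0.25 + 0.45 × 0.50 × 0.08) = 0.119 / 0.1486 = 0.80.
- Evaluable only: (0.119 / 0.680) / (0.1486 / 0.7475) = 0.88.

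The two estimates miss the truth in opposite directions, which is why both should be shown.

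**In events.** SAP Section 2.3 gives 97 randomized. With about 48 per arm and an assumed true risk of 15%, 48 × 0.15 = 7.2 events are expected in each arm. The second row would record 5.4 and 4.9; the third 4.7 and 3.6.

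**The case against.** The strongest reply is that the direction of any bias is unknown. A reader might infer that the retosiban arm will look safer. That requires retosiban to delay delivery and later births to be off site more often. The second condition is plausible, but the documents give no rate, overall or by timing, and the last three rows of the table show no bias or a slight reversal. This objection stands, and the direction must be stated as conditional.

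Other inferences also go further than the text:
- **Placental percentages are taken over all women.** Table 3.501 gives only a population label. The protocol's rule on proportions belongs to adverse events, and a summary by time to delivery is already planned for placental data.
- **FIRS can never be recorded for an off-site birth.** Another hospital's own pathology could reach the adverse event record through records review. The limit applies to study specimens.
- **Extra consent is needed for every cord sample.** Footnote 28 sits on a combined biomarker and genetic row. Footnote 24 ties additional consent to the genetic use, and Sections 3.1.4 and 6.5.2 state no such condition.
- **The whole assessment of infection is compromised, or this is the foremost risk.** Table 1 does not rank its risks. Clinical chorioamnionitis, endomyometritis, neonatal sepsis, pneumonia and meningitis do not depend on these specimens.

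Finally, safety data receive no formal test, and in this terminated trial the distortion between arms is about one event or less in the rows worked above. That limits the weight of the point. It does not make a percentage that counts unexamined women as negative a correct one.

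**Conclusion.** The point holds in a limited form. Followed as written, the plan counts women without a cord or placental specimen as free of FIRS and so understates its incidence in both arms. This assumes that some births are off site and that outside pathology does not fill the gap. If, in addition, retosiban delays delivery and late births are less often on site, the apparent RR falls to about 0.75 to 0.99 with no true effect, and a real excess is diluted. With place of delivery unrelated to timing there is no bias between arms; with late births more often on site it is 1.03 to 1.06. Only the 0.55 comes from the documents; the other inputs are assumptions.

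For placental findings the defect is an unstated denominator, not a demonstrated wrong one. Separately, the IL-6 criterion may never be measured, which would leave FIRS defined by histology in practice without the report saying so. With 97 randomized, any comparison is descriptive.

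**What to change.** In SAP Sections 8.2.3.6 and 8.2.8 and the matching displays (Tables 3.171, 3.172 and 3.501):

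1. Show, by arm, the number and percent of women with an evaluable placental or cord specimen.
2. Report FIRS and each placental finding as n/N evaluable, beside the all-women figure. State the denominator of Table 3.501.
3. Extend to FIRS the time-to-delivery summary that Section 8.2.8 already plans for placental findings. Appendix 11 lists a single placental table, so say where each breakdown will appear.
4. Report the IL-6 criterion over women with an assayed cord sample. If the stored samples are not assayed, define the reported event by histology and say so.
5. Label these rows descriptive. Having an evaluable specimen and time to delivery both arise after randomization, so neither subset is a protected randomized comparison, and the evaluable-only figure can itself be biased.

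The cost is SAP wording and a few display changes, with no new data collection, and the change can be made before database freeze. The price is a smaller N and a non-randomized subset for these rows.

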6.3.1. Liver Chemistry Stopping and Follow-Up Criteria

Blood samples will be collected for central laboratory evaluation at Screening (prior to treatment), during Day 2 of the randomized treatment phase, and at the face-to-face post-infusion assessment visit for additional liver function testing in order to ensure subject safety and to evaluate liver event etiology (in alignment with the US Food and Drug Administration premarketing clinical liver safety guidance); <http://www.fda.gov/downloads/Drugs/GuidanceComplianceRegulatoryInformation/Guidances/UCM174090.pdf>.

At Screening, before IP administration, ALT and bilirubin test results from a local laboratory should be obtained, although dosing may be started prior to the availability of these results. However, if the local laboratory results are available before the start of dosing and meet the following criteria, the subject should not be dosed and should be withdrawn from the study:

[figure not shown]
- ALT $\geq 2 \times$ ULN OR bilirubin $> 1.5 \times$ ULN ($> 35\%$ direct bilirubin). An isolated bilirubin $> 1.5 \times$ ULN is acceptable if bilirubin is fractionated and direct bilirubin is $< 35\%$.

Phase III-IV liver chemistry stopping criteria are presented in [Figure 3](#) and [Appendix 2](#).

The local and central laboratory liver function test results should be reviewed for the abnormalities shown in [Figure 3](#). If the laboratory results are not available at the start of dosing and subsequent local OR central laboratory results are abnormal, dosing may be continued at the discretion of the investigator, as long as they do not exceed the liver chemistry stopping criteria shown in [Figure 3](#) and detailed in [Appendix 2](#).

NOTE: The central laboratory report will include results for ALT, aspartate aminotransferase (AST), alkaline phosphatase (ALP), total bilirubin, and direct bilirubin.

Figure 3 Phase III-IV Liver Chemistry Stopping and Increased Monitoring Algorithm

ALT = alanine aminotransferase; INR = international normalized ratio; SAE = serious adverse event; ULN = upper limit of normal.

The complete Liver Safety Required Actions and Follow-up Assessments section can be found in [Appendix 2](#).

6.3.1.1. Study Treatment Restart or Rechallenge

Study treatment restart or rechallenge after liver chemistry stopping criteria are met by any subject participating in this study is not allowed.

6.3.2. Adverse Events

The investigator or site staff will be responsible for detecting, documenting, and reporting events that meet the definition of an AE or SAE. Separate reporting will be done for maternal, fetal, and neonatal AEs.

6.3.2.1. Definition of an AE

Any untoward medical occurrence in a patient or clinical investigation subject, temporally associated with the use of a medicinal product, whether or not considered related to the medicinal product.

Note: An AE can therefore be any unfavorable and unintended sign (including an abnormal laboratory finding), symptom, or disease (new or exacerbated) temporally associated with the use of a medicinal product. For marketed medicinal products, this

also includes failure to produce expected benefits (i.e., lack of efficacy), abuse, or misuse.

Events meeting the definition of an AE include:

- Exacerbation of a chronic or intermittent pre-existing condition including either an increase in frequency and/or intensity of the condition
- New conditions detected or diagnosed after study treatment administration even though it may have been present prior to the start of the study
- Signs, symptoms, or the clinical sequelae of a suspected interaction
- Signs, symptoms, or the clinical sequelae of a suspected overdose of either study treatment or a concomitant medication (overdose per se will not be reported as an AE/SAE) unless this is an intentional overdose taken with possible suicidal/self-harming intent. This should be reported regardless of sequelae

“Lack of efficacy” or “failure of expected pharmacological action” per se will not be reported as an AE or SAE. However, the signs and symptoms and/or clinical sequelae resulting from lack of efficacy will be reported if they fulfill the definition of an AE or SAE.

Events that **do not** meet the definition of an AE include:

- Medical or surgical procedure (e.g., endoscopy, appendectomy); the condition that leads to the procedure is an AE
- Situations where an untoward medical occurrence did not occur (social and/or convenience admission to a hospital)
- Anticipated day-to-day fluctuations of pre-existing disease(s) or condition(s) present or detected at the start of the study that do not worsen

The disease/disorder being studied, or expected progression, signs, or symptoms of the disease/disorder being studied, unless more severe than expected for the subject’s condition.

